17.4.3 Other analyses

Efficacy

For cohort I, in the first year of the safety extension trial period the derivation formula for HV is: (height at 104 weeks visit-height at 52 weeks visit) / (time from 52 weeks visit to 104 weeks visit in years).

For HV in the second year of the safety extension trial period the derivation formula is: (height at 156 weeks visit - height at 104 weeks visit) / (time from 104 weeks visit to 156 weeks visit in years).

For HV in the first year of long-term safety extension trial period the derivation formula is: (height at 208 weeks visit-height at 156 weeks visit) / (time from 156 weeks visit to 208 weeks visit in years).

For HV in the third year of the long-term safety extension trial period the derivation formula is: (height at 312 weeks visit-height at 208 weeks visit) / (time from 260 weeks visit to 312 weeks visit in years).

For HV in the fourth year of the long-term safety extension trial period the derivation formula is: (height at 364 weeks visit-height at 312 weeks visit) / (time from 312 weeks visit to 364 weeks visit in years).

HV will be calculated for each year in the extension until NNC0195-0092 is available for prescription, in the same way as for the previous years.

For cohort II and III, HV at week 52 the derivation formula is: (height at 52 weeks visit-height at baseline (0 week visit 2) / (time from baseline (0 week visit 2) to 52 weeks visit in years).

For HV in the second year of the long-term safety extension trial period the derivation formula is: (height at 104 weeks visit-height at 52 weeks visit) / (time from 104 weeks visit to 52 weeks visit in years).

For HV in the third year of the long-term safety extension trial period the derivation formula is: (height at 156 weeks visit - height at 104 weeks visit) / (time from 104 weeks visit to 156 weeks visit in years).

For HV in the fourth year of the long-term safety extension trial period the derivation formula is: (height at 208 weeks visit-height at 156 weeks visit) / (time from 156 weeks visit to 208 weeks visit in years).

HV will be calculated for each year in the extension until NNC0195-0092 is available for prescription in the same way as for the previous years.

HV at week 52 (cohort II and III), 104, 156, 208, 260, 312, 364 (the latter for cohort I) and every year until the end of the extension until NNC0195-0092 is available for prescription for children with GHD or August 2024 at the latest will be analysed using descriptive statistics.

Changes from baseline (week 0) in HV SDS, height SDS, IGF-I SDS and IGFBP-3 SDS to week 52 (cohort II and III), 104, 156, 208, 260, 312, 364 (the latter for cohort I) and every year until the end of the extension until NNC0195-0092 is available for prescription for children with GHD or August 2024 at the latest will be analysed using descriptive statistics.

Near adult height (NAH) is defined as HV < 2 cm/year calculated over a period of at least 9 months AND for males: have reached a bone age of ≥ 16 years; for females: have reached a bone age of ≥ 14 years. If bone age is not available, then NAH is defined as HV < 2 cm/year calculated over a period of at least 9 months AND a chronological age of ≥ 17 years for males and a chronological age of ≥ 15 years for females. For subjects who have reached NAH in the long-term safety extension trial period the following variables will also be analysed using descriptive statistics: NAH SDS, change from baseline (week 0) to the year NAH is reached in height SDS, midparental target height SDS and index of genetic height potential (derived from midparental target height SDS and NAH SDS).

Bone age (X-Ray of left hand and wrist, centrally assessed according to Greulich & Pyle atlas)¹⁹ progression vs. chronological age at week 104 and 156, 208, 260, 364 (the latter for cohort I) and every year until the end of the extension until NNC0195-0092 is available for prescription for children with GHD or August 2024 at the latest will be analysed using descriptive statistics.

PRO data (cohort I):

Changes from baseline (week 0) in emotional well-being score, physical health score, social well-being core and total score from baseline to week 104, and 156, 208, 260, 312 and 364 in TRIM-CGHD-O (Treatment Related Impact Measure – Child Growth Hormone Deficiency- Observer) will be analysed using descriptive statistics.

Total score of TB-CGHD-O (The Treatment Burden Measure – Child Growth Hormone Deficiency – Observer) and total score of TB-CGHD-P (The Treatment Burden Measure – Child Growth Hormone Deficiency – Parent/Guardian) at week, 104 and 156, 208, 260, 312 and 364 will be analysed using descriptive statistics.

The scores of the PROs ranges from 0-100. A lower score indicates a better health state.

For subjects switching from Norditropin® to NNC0195-0092 GH-PPQ (The Growth Hormone Patient Preference Questionnaire-Parent/Guardian) at week 160 will be analysed using descriptive statistics. Answers are scored on a 5 levels scale from 'Not at all' to 'Extremely' or from 'Never' to 'All of the time'.

Safety

The following will be described using descriptive statistics for up to the end of the extension until NNC0195-0092 is available for prescription or August 2024 at the latest:

Incidence of technical complaints, including injection site reactions

Changes from baseline to week 26, 52, 104, 156, 260, 364 (the latter for cohort I) and every year until the end of the extension until NNC0195-0092 is available for prescription for children with GHD or August 2024 at the latest in physical signs and vital signs

Changes from baseline to week 26, 52, 104, 156, 260, 364 (the latter for cohort I) and every year until the end of the extension until NNC0195-0092 is available for prescription for children with GHD or August 2024 at the latest in clinical safety laboratory parameters, including haematology,

biochemistry, hormones (e.g. fasting serum cortisol, thyroid function test), lipids, fasting glucose, fasting insulin, and HbA1c levels

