4.1 Objectives

4.1.1 Cohort I

Primary objective:

- To evaluate the efficacy of multiple dose regimens of once-weekly NNC0195-0092 after 26 weeks of treatment in GH treatment naïve pre-pubertal children with GHD, compared to once-daily hGH administration (Norditropin® FlexPro®).

Secondary objectives:

- To evaluate the safety of multiple dose regimens of once-weekly NNC0195-0092 during 26 weeks of treatment in GH treatment naïve pre-pubertal children with GHD.
- To evaluate the efficacy and safety of multiple dose regimens of once-weekly NNC0195-0092 for up to 364 weeks of treatment in GH treatment naïve pre-pubertal children with GHD, compared to Norditropin® FlexPro®.
- To investigate the impact of NNC0195-0092 relative to Norditropin® FlexPro® on wellbeing, psychosocial functioning, treatment satisfaction and preference in GH treatment naïve pre-pubertal children with GHD by using patient reported outcome (PRO) questionnaires.
- To monitor NNC0195-0092 and Norditropin® PK throughout the trial.

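### Cohort I, year 3 of the long-term extension: the height velocity formula divides 104 weeks of growth by 52 weeks, and year 2 has no formula although height velocity at week 260 is planned

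*Combined protocol and SAP*

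**What the plan says.** Section 17.4.3 (Other analyses, Efficacy) gives one HV formula per year for cohort I. For year 1 of the long-term extension it is "height at 208 weeks visit-height at 156 weeks visit) / (time from 156 weeks visit to 208 weeks visit in years", and for year 4 it is "height at 364 weeks visit-height at 312 weeks visit) / (time from 312 weeks visit to 364 weeks visit in years". For year 3 it is "height at 312 weeks visit-height at 208 weeks visit) / (time from 260 weeks visit to 312 weeks visit in years". No cohort I line is given for year 2.

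The only formula labelled as the second year of the long-term extension comes after the list turns to cohorts II and III, and it uses weeks 52 and 104: "For HV in the second year of the long-term safety extension trial period the derivation formula is: (height at 104 weeks visit-height at 52 weeks".

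The same section then plans descriptive summaries of "HV at week 52 (cohort II and III), 104, 156, 208, 260, 312, 364 (the latter for cohort I", and at the same weeks "Changes from baseline (week 0) in HV SDS, height SDS, IGF-I SDS and IGFBP-3 SDS". HV in the later extension, beyond week 364, is to be calculated as in the preceding years.

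**The concern.** An annual velocity needs the growth and the elapsed time to refer to the same interval. In the year-3 line they do not: two years of growth are divided by one year. If programmed as written, HV at week 312 is inflated for every child with positive growth in year 2. The change in HV SDS at week 312 inherits the error if it is built on the same HV. HV at week 260 is a planned output with no stated derivation.

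After week 156 these yearly values are the descriptive record of growth on long-term treatment. It is reasonable to read them as bearing on the cohort I secondary objective in Section 4.1.1, "To evaluate the efficacy and safety of multiple dose regimens of once-weekly NNC0195-0092 for up to 364 weeks of treatment". A false spike in year 3, next to an undefined year 2, would misstate the growth course.

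**Working it through.** The plan states no numerical result that depends on this formula, so there is no figure to reproduce. The check compares the intervals and then sizes the error.

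**Intervals in the cohort I formulas (Section 17.4.3)**

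| Year | Height gain over weeks | Divided by time over weeks |
|---|---|---|
| Safety extension, year 1 | 52–104 | 52–104 |
| Safety extension, year 2 | 104–156 | 104–156 |
| Long-term extension, year 1 | 156–208 | 156–208 |
| Long-term extension, year 2 | none given | none given |
| Long-term extension, year 3 | **208–312** | **260–312** |
| Long-term extension, year 4 | 312–364 | 312–364 |

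**Size of the error.** Let g2 and g3 be the growth (cm) in weeks 208–260 and 260–312, and T the time from the week-260 visit to the week-312 visit.

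- As written: (g2 + g3)/T
- Matched intervals: g3/T
- Ratio: 1 + g2/g3

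T cancels. Table 2-3 sets these visits at week + 1 day with a +3 day window, so T runs from 361 to 367 days, but it is the same in both versions.

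The documents give no growth rates for these years. The values below are assumptions:

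| g2, g3 (cm) | Ratio |
|---|---|
| 5, 5 | 10/5 = 2.00 |
| 6, 5 | 11/5 = 2.20 |
| 5, 7 | 12/7 = 1.71 |
| 6, 4 | 10/4 = 2.50 |
| 5, 3 | 8/3 = 2.67 |
| 4, 8 | 12/8 = 1.50 |

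For g2/g3 between 0.7 and 1.5 the ratio runs from 1.7 to 2.5. The last two rows show that those are not outer limits.

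**Constant growth rate with actual visit days.** If the rate rather than the yearly gain is held fixed, the ratio is the time from week 208 to week 312 divided by T. At nominal visits this is 728/364 = 2.00. At the extremes of the windows it is 728/367 = 1.98 and 728/361 = 2.02.

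**Reported series at a steady 5 cm/year:** year 1, about 5; year 2, no formula; year 3, about 10; year 4, about 5.

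**HV SDS, conditional.** This applies only if HV SDS at week 312 uses the same HV. The reference SD is not in the documents. With an assumed range of 0.8 to 1.5 cm/year, an excess of 5 cm/year adds 5/0.8 = 6.3 to 5/1.5 = 3.3 SDS.

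**Could the fault lie in the denominator?** Weeks 208–312 in both places would give a two-year average, not the HV of the third year that the line is labelled to give.

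**The case against.** The strongest reply is that the intent is plain. Every neighbouring formula uses a single 52-week interval, and both the year-3 label and its denominator point to weeks 260–312. The natural reading is one mistyped week number and one omitted line. An analyst following the pattern would avoid the error, and a doubled value would probably be noticed. Section 17 also allows a more technical analysis plan, if one is thought necessary. All of this is fair, and it limits the likelihood of harm. It does not make the written rule correct or supply the missing one, and nothing in the documents corrects either.

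The link to the 364-week objective can also be challenged. Section 4.2.2.1 names HV only up to week 52, Section 17.4.1 ties that objective to changes up to week 52, and Section 5.2 says the long-term extension was added for long-term safety and near-adult-height data. The link is therefore an inference. Neither the error nor the fix depends on it.

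The SDS figure is the softest number. Children entered at 2.5 to 10 years (Section 6.2.1), so at week 312, six years on, they are roughly 8.5 to 16. One SD range over that span is only illustrative.

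The effect is confined to descriptive summaries. The primary endpoint (Section 17.3.1), the week-52 mixed models (Section 17.4.1) and height SDS are untouched. So is the near-adult-height rule, which has its own HV period of at least 9 months. All subjects receive NNC0195-0092 by then, so no concurrent treatment comparison is distorted.

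**Conclusion.** The point holds. The cohort I year-3 formula is wrong as written, and the year-2 formula is absent although HV at week 260 is planned. Followed literally, it returns 1 + g2/g3 times the true year-3 HV, which is 2.0 times under constant growth. The direction is certain whenever growth in both years is positive. The exact multiple depends on growth rates that the documents do not give, and the SDS effect also depends on an assumed reference SD and on HV SDS sharing this derivation. The error should be corrected, but it does not threaten the trial's main conclusions.

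**What to change.** In Section 17.4.3, for cohort I:

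- **Year 3:** (height at week 312 − height at week 260) / (years from the week-260 visit to the week-312 visit).
- **Year 2 (new line):** (height at week 260 − height at week 208) / (years from the week-208 visit to the week-260 visit).
- State that HV SDS at these weeks is based on the same HV.

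In the same edit, tidy the cohort II and III year-2 denominator, where "time from 104 weeks visit to 52 weeks visit in years" gives the two visits in reverse order. That is a matter of wording only.

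The cost is a short text correction. No new data are needed: Table 2-3 already schedules height at weeks 208, 260 and 312. It should be in place before the week-364 analysis is programmed.

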End of treatment							x	
Sign off Casebook								x

¹ Visit to be performed when NNC0195-0092 is available for prescription for children with GHD or August 2024, at the latest. Visit 38 will be no later than week 442.

² Visit should take place 1-4 days after trial drug administration.

³ Trial drug should be administered 4-6 days prior to last site visit to ensure wash out prior to antibody test.

⁴ The follow-up visit should take place 30 days after last treatment.

⁵ Collected if performed as per local practice.

⁶ Only for female subjects having menarche during the trial.

⁷ If X-ray and ECG were performed within 6 months prior to the end of treatment visit, these should not be performed at the end of treatment visit.

Table 2-5 Flow chart long-term safety extension trial period (cohort II FOR SWEDEN ONLY not applicable as no subjects will be enrolled into cohort II END OF TEXT FOR SWEDEN ONLY and III FOR INDIA ONLY not applicable as no subjects will be enrolled into cohorts II and III END OF TEXT FOR INDIA ONLY)

Trial Periods	Protocol section	Information for cohort II & III	Screening for cohort II & III	Long-term safety extension trial period																	End of treatment	Follow-up
				1	2	17	18	19	20 ²	21	22	23	24 ²	25	26	27	28 ²	29	30	31		
Visit number		0	1																		32 ^{4,12}	
Timing of visit Weeks		- 1 day minimum	-3 to -2	0	13	26	39	52+1 day	65	78	91	104+ 1 day	117	130	143	156+ 1 day	169	182	195	Last treatment + 5 days	End of treatment + 30 days	
Visit window Days					± 7	± 7	± 7	+ 3	± 7	± 7	± 7	+ 3	± 7	± 7	± 7	+ 3	± 7	± 7	± 7	± 1	+ 2	
Demography	8.4.1		x																			
Medical history ¹	8.4.2		x																			
EFFICACY																						
Body measurements																						
Height/Length	8.5.1.1 / 8.5.1.2		x	x	x	x	x	x	x	x	x	x	x	x	x	x	x	x	x	x		
Body weight	8.5.1.3		x	x	x	x	x	x	x	x	x	x	x	x	x	x	x	x	x	x		
Biomarkers																						
IGF-I	8.7.7		x			x		x		x		x		x		x		x		x	x	
IGFBP-3	8.7.7		x			x		x		x		x		x		x		x		x	x	
PK Sampling	8.7.8			x					x			x		x		x		x		x	x	

Trial Periods	Protocol section	Information for cohort II & III	Screening for cohort II & III	Long-term safety extension trial period																		End of treatment	Follow-up
				0	1	2	17	18	19	20 ²	21	22	23	24 ²	25	26	27	28 ²	29	30	31	32 ^{4,12}	
Visit number		0	1	2	17	18	19	20 ²	21	22	23	24 ²	25	26	27	28 ²	29	30	31	32 ^{4,12}			

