In the main trial period of the study sixty (60) subjects will be randomised in a 1:1:1:1 (████ mg/kg/week NNC0195-0092: ████████ mg/kg/week NNC0195-0092: ████████ mg/kg/week NNC0195-0092: ████████ mg/kg/day Norditropin® FlexPro®) manner to receive either NNC0195-0092 or

Norditropin® FlexPro®. After week 52 all subjects in the NNC0195-0092 arm are switched to [REDACTED] mg/kg/week. After week 156 all subjects on Norditropin® FlexPro® are switched to NNC0195-0092 ([REDACTED] mg/kg/week).

In the long-term safety extension trial period subjects from two additional age groups will be enrolled, cohort II (< 2 years and 26 weeks at screening) and cohort III (> 9 years (girls)/>10 years (boys) and ≤ 17 years at screening) and will be treated with once-weekly NNC0195-0092 ([REDACTED] mg/kg/week). They will start treatment at visit 2 where after they will continue the visit schedule for the long-term safety extension (visit 17 and onwards). Subjects in cohorts II and III will be treated with NNC0195-0092, [REDACTED] mg/kg/week until latest August 2024 (expected last end-of-treatment visit for cohort I) (for details, see Section [8.3.3](#)). As recruitment of subjects from these age groups may be challenging, enrolment of subjects naïve and non-naïve to GH treatment until 4 months prior to expected last end-of-treatment visit for cohort I is possible, unless recruitment has already been completed.

Data from the trial for cohort I will be analysed when all subjects have completed the 26, 52, 104 and 156 and 364 weeks of treatment. For subjects continuing treatment until NNC0195-0092 is available for prescription in their country or August 2024 at the latest, the additional data collected between week 364 (visit 32) and the end-of-treatment visit (visit 38) will be analysed additionally. Further interim reporting may be performed including cohort II and III in association with marketing authorisation application or in connection with Health Authorities e.g. FDA, EMA and PMDA requirement for/during the regulatory review. Final analysis will take place when all subjects have completed the trial.

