- Accidental administration of a higher dose than intended. That is a dose higher than 100 % more than the intended dose; however the administered dose must deviate from the intended dose to an extent where clinical consequences for the trial subject were likely to happen as judged by the investigator, although they did not necessarily occur.

Technical complaint

A technical complaint is any written, electronic, or oral communication that alleges product (medicine or device) defects. The technical complaint may be associated with an AE, but does not concern the AE itself.

Examples of technical complaints:

- The physical or chemical appearance of trial products (e.g. discoloration, particles or contamination)
- The packaging material (e.g. leakage, cracks, rubber membrane issues or errors in labelling text)
- Problems related to devices (e.g. to the injection mechanism, dose setting mechanism, push button or interface between the pen and the needle)

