Data management is the responsibility of Novo Nordisk.

Appropriate measures, including encryption of data files containing person identifiable data, will be used to ensure confidentiality of subject data, when they are transmitted over open networks.

Data from central laboratories will be transferred electronically. In cases where data is transferred via non-secure electronic networks, data will be encrypted during transfer.

The subject and any biological material obtained from the subject will be identified by subject number and trial ID. Appropriate measures such as encryption or leaving out certain identifiers will be enforced to protect the identity of subjects in all presentations and publications as required by local, regional and national requirements.

DBLs are planned during the trial, facilitating analysis of the 26 weeks main trial period, 52 weeks extension trial period and 104 and 156 weeks safety extension trial period the 364 weeks long-term safety extension period and the 'extension until NNC0195-0092 is available for prescription for children with GHD period' data. Further interim reporting may be performed in association with marketing authorisation application or in connection with Health Authorities e.g. FDA, EMA and PDMA requirement for/during the regulatory review. The final DBL will occur after the 208 week long-term safety extension trial period (368 weeks) is completed.

16 Computerised systems

Novo Nordisk will capture and process clinical data using computerised systems that are described in Novo Nordisk Standard Operating Procedures and IT architecture documentation. The use and control of these systems are documented.

Investigators working on the trial may use their own electronic systems to capture source data.

17 Statistical considerations

If necessary, a statistical analysis plan (SAP) may be written in addition to the protocol, including a more technical and detailed elaboration of the statistical analyses. The SAP will be finalised before the first pDBL.

Biostatistics, Novo Nordisk, will be responsible for the statistical analyses.

The one-sided test used for the primary endpoint is based on an alpha level of 2.5%. All other statistical tests conducted will be two sided on the 5% significance level. Age group is defined as a factor with 2 levels: <6 years ≥ 6years. No adjustment for multiple testing will be applied.

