17.4.2 Supportive secondary safety endpoints (cohort I)

The following endpoints will be used to support the secondary objectives of evaluation of safety for up to 364 weeks of treatment:

- Incidence of adverse events, including injection site reactions
- Occurrence of anti-NNC0195-0092 and anti-hGH antibodies

Adverse events will be analysed using descriptive statistics. All adverse events with onset after the first administration of trial product and up until week 26 or 14 days after last trial drug administration, whichever comes first, will be included in the main trial period analysis. The adverse events will be summarised by treatment, MedDRA (Medical Dictionary for Regulatory Activities) system organ class and MedDRA preferred term. The descriptive statistics will include the number and percentage of subjects who experienced adverse events, the number of events and rate. Adverse events will be listed by treatment and subject with information on severity, relationship to trial product and demographics. Similar tables will be done for adverse events with onset after the first administration of trial product and up until week 52 for the extension trial period and for adverse events with onset after the first administration of trial product and up until week 104 and 156 , respectively, for the safety extension, and for adverse events with onset after the first administration of trial product and up until week 260 and 364 for the long-term safety extension trial period and follow-up period analysis.

Adverse events with onset 14 days or more after last trial drug administration will be reported in a separate listing. Adverse events with onset before first dosing will be reported in a separate listing.

All other safety endpoints will be analysed using descriptive statistics.

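### Cohort I adverse-event tables end at week 364 although treatment can continue with visit 38 as late as week 442, and the safety list covering that extension names technical complaints but not adverse-event incidence or antibody occurrence

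*Combined protocol and SAP*

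**What the plan says.** Section 17.4.2 frames the cohort I safety endpoints with a time limit: "The following endpoints will be used to support the secondary objectives of evaluation of safety for up to 364 weeks of treatment". The endpoints are "Incidence of adverse events, including injection site reactions" and antibody occurrence. Adverse-event tables then count from first dose to successive cut-offs at weeks 26, 52, 104 and 156, and the last two run "up until week 260 and 364 for the long-term safety extension trial period and follow-up period analysis". Events starting 14 days or more after the last dose go to a separate listing.

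Sections 1 and 5.3 allow cohort I subjects to continue after week 364 until the product can be prescribed in their country, or until August 2024. Table 2-4, footnote 1, sets the limit: "Visit 38 will be no later than week 442". The same table schedules adverse events and injection site reactions at every visit, including follow-up, and antibodies at visits 36 and 38.

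The safety part of section 17.4.3 runs to the end of that extension and has three items: "Incidence of technical complaints, including injection site reactions", changes in physical and vital signs, and changes in laboratory parameters. On the first item, section 12.1 says: "A technical complaint is any written, electronic, or oral communication that alleges product (medicine or device) defects". It adds that a complaint may accompany an adverse event but is not about the event itself.

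Section 5.1 says that, for continuing subjects, "the additional data collected between week 364 (visit 32) and the end-of-treatment visit (visit 38) will be analysed additionally".

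**The concern.** Adverse-event incidence is the main safety outcome of the plan, yet the specified tables stop where the longest exposures begin. A programmer who follows 17.4.2 and 17.4.3 to the letter would tabulate product complaints, vital signs and laboratory values for the post-364 period. That programmer would produce no incidence table of adverse events (injection site reactions apart) and no summary of antibody occurrence.

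The technical-complaints line does not make sense as worded. Sections 4.2.1.2, 4.2.2.2, 17.3.2 and 17.4.2 all place injection site reactions under adverse events, and the definition in 12.1 keeps the two concepts apart.

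The data monitoring committee stops work after the safety extension (section 12.7.2). In the later years, planned tables therefore carry more of the weight of showing a long-term safety signal.

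**Working it through.** **1. Reproduce the week-442 limit.** Table 2-4 places visits 33 to 37 at weeks 377, 390, 403, 416 and 429, that is, 364 + 13k for k = 1 to 5. The next step is 429 + 13 = 442, which is the stated limit for visit 38.

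**2. Size of the gap.** 442 − 364 = 78 weeks, about 1.5 years. As a share of the longest span, 78/442 = 17.6%.

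**3. Dosing within the gap.** Table 2-4, footnote 3, puts the last dose 4 to 6 days before the last site visit.
- Last dose: 442 − 6/7 = 441.14 to 442 − 4/7 = 441.43 weeks.
- Dosing past week 364: 77.1 to 77.4 weeks.
- Adding 14 days after the last dose: 79.1 to 79.4 weeks.
- Adding the 30-day follow-up instead: 81.4 to 81.7 weeks.

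**4. What is collected after week 364, against what is summarised (cohort I).**

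| Outcome | Collected (Table 2-4) | Named summary after week 364 |
|---|---|---|
| Adverse events other than injection site reactions | Every visit and follow-up | None; last table in 17.4.2 is cut at week 364 |
| Injection site reactions | Every visit and follow-up | Incidence, under the technical-complaints line of 17.4.3 |
| Anti-drug antibodies | Visits 36 and 38 | None |
| Vital signs, physical examination, laboratory | Visits 34, 36, 38 | Yearly changes, 17.4.3 |
| Height velocity, height SDS, IGF-I SDS, IGFBP-3 SDS, bone age | As scheduled | Yearly, 17.4.3 |

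The plan thus carries the other main outcomes past week 364 by name, but not these two.

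**5. Subjects who end at visit 32.** Table 2-3 schedules this visit at week 364 + 5 days, with the last dose 4 to 6 days before. On the nominal day, the last dose falls between 5 − 6 = −1 and 5 − 4 = +1 day of week 364. Nearly all of the 14 days after the last dose therefore lie beyond the week-364 cut. Events in those days also start too early for the listing of events at 14 days or more. They reach the general by-subject listing, but no specified incidence table, although 17.4.2 labels that analysis as covering the follow-up period too.

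**The case against.** The strongest reply is that nothing is lost. Section 5.1 commits to analysing the data after week 364, section 15 plans a database lock for that period, and 17.4.2 provides by-subject listings. The cohort I safety objective and endpoints are also limited to 364 weeks, so tables ending there match them. This stands in part: a reader might infer that the plan means to ignore the later adverse events, and it does not. But a general promise names no output, a listing is not an incidence summary, and 17.4.3 takes other outcomes past week 364 explicitly.

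A reader might infer that technical complaints were typed in error for adverse events. The parallel wording elsewhere makes this plausible, but it remains an inference. Technical complaints are collected in their own right (section 12.4.1), and the line may be a genuine item badly worded. Adverse-event incidence is missing either way.

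A reader might infer that the week-364 cut breaks the 14-day rule of the main period. It does not. That rule counts to week 26 or 14 days after the last dose, whichever comes first, so it never extends a window past the period cut.

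A reader might infer a premature lock from "The final DBL will occur after the 208 week long-term safety extension trial period (368 weeks) is completed". The documents do not support that either. The same section plans a lock for the later extension, and cohorts II and III, who are part of the long-term extension, may be treated until August 2024. Section 5.1 also places the final analysis after all subjects have completed the trial, and section 7 ends the trial at the last follow-up visit. The figure of 368 weeks is at most stale.

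**Conclusion.** The gap is real and should be closed before the post-364 data are reported. No specified table gives cohort I adverse-event incidence (other than injection site reactions) or antibody occurrence after week 364, and the one incidence line that reaches the later period conflicts with the protocol's own definition of a technical complaint. The size is a ceiling of 78 weeks, about 77 with dosing. It applies only to cohort I subjects who continue; the documents do not give their number. A smaller gap of about two weeks after the last dose affects subjects who end at visit 32, if the week-364 cut is applied literally. Cohorts II and III are not affected, because section 17.3.2 sets their window by the end of trial or the last dose.

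This rests on taking Table 2-4 and the continuation text of section 5.3 as operative. Section 5.3 also states a maximum treatment duration of 364 weeks for a single subject, and these statements must be reconciled. It also assumes that no other document specifies the missing tables. Section 17 makes a separate SAP optional and has it finalised before the first partial database lock.

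**What to change.** - In 17.4.3 (Safety), list "Incidence of adverse events, including injection site reactions" and the occurrence of anti-NNC0195-0092 and anti-hGH antibodies, to the end of the extension. Give technical complaints a separate line without injection site reactions.
- In 17.4.2, add a final cohort I adverse-event table running to the end-of-trial visit or 14 days after the last dose, whichever comes first, as in 17.3.2. Later events stay in the existing separate listing. State that the end-of-trial visit here means the 30-day follow-up visit. If it were read as visit 32 or visit 38, the window would close about 5 days after the last dose.
- In section 15, reconcile the 368-week figure for the final lock with the lock planned for the extension.

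The cost is a wording change and one more run of existing table programs. The data are already collected.
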